# 9.3. Statistical Analyses

### 9.3.1. General Considerations

In general, data collected will be listed together with appropriate derived variables. Descriptive statistical methods will be used to analyze safety and efficacy data. Where appropriate, this may include summaries and graphical displays by time point.

Summaries will be provided by treatment assignment and overall. Summaries will include the number of observations (n), mean, SE, 95% CI, median, quartiles, minimum, and maximum for continuous measures and categorical measures sample size, frequencies, and percentages. P-values for comparing treatment groups may be provided, but these should be interpreted as supportive summary statistics.

The baseline value will be the last assessment before the first IMP administration.

All study visits will be recalculated based on actual dates. The rules for calculating the analysis visits will be documented in the SAP. Rules for imputing partial dates or missing dates will be provided in the SAP.

## 9.3.2. Primary Endpoint Analysis

The primary endpoint is response on  $\geq 3$  of 5 items of CRESS at week 24. The 5 items are systemic disease activity (clinESSDAI), patient-reported symptoms (ESSPRI), tear gland function (Schirmer's test, OSS), salivary gland function (UWSF, SGUS), and serology (serum IgG and RF).

A 95% Wilson Score CI for the proportion of CRESS responders will be presented for both treatment groups. This will be provided for all full analysis set participants and by IgG stratum at screening (> 16.0 g/L or  $\leq 16 \text{ g/L}$ ) for the efgartigimod treatment group.

Additionally, the CRESS response will be analyzed between efgartigimed and placebo using the full analysis set by means of a Cochran-Mantel-Haenszel test, stratified by IgG value at screening (> 16.0 g/L or  $\leq 16 \text{ g/L}$ ). The common odds ratio will be provided, along with the 95% CI.

In the event of missing values for the primary endpoint, only those participants who have a week 24 value will be included in the primary analysis. A sensitivity analysis, treating those participants with missing week 24 data as nonresponders, will be included.

## 9.3.3. Secondary Endpoint Analyses

The proportion of responders at week 24 in the clinESSDAI and ESSPRI components of the CRESS will be analyzed using the same approach as the overall CRESS response. The ESSDAI and STAR responder endpoints will be analyzed similarly.

Descriptive summaries by time point of the CRESS components, the ESSDAI and STAR scores, their changes, and percent changes from baseline will be provided, as appropriate. Estimates of the differences in response between treatment groups will be provided based on an analysis of covariance (ANCOVA), or suitable alternative, approach.

The histological parameters, relative counts of lymphocytic infiltrate (stained for CD45), and B/B+T cell ratio will be summarized descriptively as raw counts and their changes from baseline.

Full details of the secondary analyses will be included in the SAP.

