# 6.3. Assignment to Study Intervention

All participants will be randomized to IMP using IRT in a 2:1 ratio of efgartigimod or placebo, respectively.

Upon confirmation of eligibility at baseline, the participant will be randomized through IRT and stratified by IgG value at screening (> 16.0 g/L or  $\leq 16 \text{ g/L}$ ).

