## **8.2.1. CRESS**

The primary efficacy endpoint is the proportion of responders on  $\geq 3$  of 5 items at week 24 using CRESS. CRESS has been developed to assess treatment efficacy in participants with pSS. CRESS consists of the following items, with definitions of treatment response and lower disease activity:

- Systemic disease activity: as measured with clinESSDAI (Section 8.2.4)
  - Response is defined as a score of < 5 points.
- Patient-reported symptoms: as measured with ESSPRI (Section 8.2.6.1)
  - Response is defined as a decrease of  $\geq 1$  point or  $\geq 15\%$  from baseline.
- Tear gland function: as measured with Schirmer's test (Section 8.2.7.3) and OSS (Section 8.2.7.4)
  - If Schirmer's test is ≤ 5 mm at baseline (abnormal), a response is defined as an increase of at least 5 mm from baseline. OR
  - If OSS is ≥ 3 points at baseline (abnormal), a response is defined as a decrease of at least 2 points from baseline. OR
  - If both OSS and Schirmer's scores are normal at baseline, a response is defined as no change that results in an abnormal OSS or Schirmer's score.
- Salivary gland function: as measured with UWSF (Section 8.2.7.1) and SGUS
  - UWSF: at least 25% increase in score, or if score is 0 mL/min at baseline, any increase from baseline OR
  - SGUS: at least 25% decrease in total Hocevar score from baseline
- Serology: as measured with serum IgG and RF
  - RF: Decrease of at least 25% from baseline OR
  - IgG: Reduction of at least 10% from baseline

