# 9.5. Sample Size Determination

Participants will be randomized in a 2:1 ratio (efgartigimod:placebo) to achieve approximately 15 randomized participants with an IgG value at screening > 16.0 g/L and 15 participants without an IgG value at screening > 16.0 g/L.

Assuming 50% of the 20 randomized efgartigimod participants are CRESS responders, the 95% 1-sided confidence limit lower bound for the proportion of responders is approximately 33% (Wilson score interval). Placebo response rates ranging from 24% to 32% have been reported. Therefore the target sample size should provide sufficient precision of the efgartigimod treatment effect at week 24 for planning future studies.

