#### Statistical Analysis Plan

Page 49 of 78

Biological [1]	No=0	Absence of any of the following biological features
	Low=1	Clonal component and/or hypocomplementemia (low C4 or C3 or CH50) and/or hypergammaglobulinemia or high IgG level between 16 and 20 g/L
	Moderate=2	Presence of cryoglobulinemia and/or hypergammaglobulinemia or high IgG level > 20 g/L, and/or recent onset hypogammaglobulinemia or recent decrease of IgG level (< 5 g/L)

The proportion of efgartigimod and placebo participants with improvement of >= 3 points in score and the proportion of participants having ESSDAI score of <5 at week 24 will be provided, along with 95% Wilson Score CIs by each IgG stratum at screening (> 16.0 g/L or  $\leq$  16 g/L) for both treatment groups and for each of these two endpoints.

# 14.2.1.2 Proportion of Participants with Minimal Clinically Important Improvement in clinESSDAI: Improvement of ≥ 3 Points in clinESSDAI Score at Week 24 and Proportion of oParticipants with Low Disease Activity: clinESSDAI score of < 5 at Week 24

As explained in Section 14.1.1 of SAP, the ClinESSDAI includes all ESSDAI domains except the biological domain.

The proportion of efgartigimod and placebo participants with improvement of  $\geq$  3 points in clinESSDAI score and the proportion of participants having clinESSDAI score of  $\leq$  5 at week 24 will be provided, and along with 95% Wilson Score CIs by each IgG stratum at screening ( $\geq$  16.0 g/L or  $\leq$  16 g/L) for both treatment groups and for each of these two endpoints.

### 14.2.1.3 Proportion of Participants with Minimal Clinically Important Improvement in ESSPRI: Decrease of 1 Point or ≥ 15% at Week 24

The Information on the derivation of ESSPRI total score is provided in Section 14.1.1.

The proportion of participants with decrease of 1 point or  $\geq$  15% in ESSPRI total score at week 24 will be provided and along with 95% Wilson Score CIs by each IgG stratum at screening ( $\geq$  16.0 g/L or  $\leq$  16 g/L) for both treatment groups and for each of these two endpoints.

#### 14.2.1.4 Change in ESSDAI Score, clinESSDAI Score and ESSPRI Score at Week 24

These scores will be descriptively summarized for actual scores and changes from baseline scores for each visit and by treatment.

Document:

Author:

Version Number: V2.0

Version Date: 31JAN2024

Template No.: CS TP BS016 Revision 7 Reference: CS WI BS005

Effective Date: 01Nov2021

Statistical Analysis Plan

Author:

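### The two secondary endpoints defined as a score below 5 at week 24 (ESSDAI and clinESSDAI) are compared between arms without the baseline score, which costs precision in a trial of about 20 versus 10

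*Protocol*

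**What the plan says.** **Method.** Protocol 9.3.2 compares CRESS response between arms by a "Cochran-Mantel-Haenszel test, stratified by IgG value at screening", with a common odds ratio and 95% CI. Protocol 9.3.3 extends this to the secondary responders: the proportion responding "in the clinESSDAI and ESSPRI components of the CRESS will be analyzed using the same approach as the overall CRESS response", and "The ESSDAI and STAR responder endpoints will be analyzed similarly". For the two low-disease-activity endpoints, SAP 14.2.1.1 and 14.2.1.2 show only proportions with Wilson intervals by IgG stratum in each arm; for example, "the proportion of participants having ESSDAI score of <5 at week 24 will be provided".

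**Endpoint type.** ESSDAI < 5 and clinESSDAI < 5 at week 24 are fixed levels. The clinESSDAI item of CRESS uses the same cut: "Response is defined as a score of < 5 points" (protocol 8.2.1).

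**Balance.** Under protocol 6.3, "the participant will be randomized through IRT and stratified by IgG value at screening". No disease-activity score is a stratification factor. Entry requires ESSDAI of at least 5 (protocol 5.1) and sets no upper limit on the score.

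**Baseline data.** SAP section 9 tabulates baseline ESSDAI, an ESSDAI ≥ 10 split and baseline clinESSDAI.

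**Continuous scores.** Protocol 9.3.3 also mentions ANCOVA or an alternative, directly after the sentence on summaries of scores and their changes. SAP 14.2.1.4 carries this out as an MMRM of change in ESSDAI, clinESSDAI and ESSPRI.

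**The concern.** A participant who enters at 6 needs to fall by only 2 points to be below 5. One who enters at 14 needs to fall by 10. For an absolute threshold, the starting score is plausibly the strongest measured predictor of response, whatever the treatment.

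With about 20 and 10 participants, one arm can easily start lower by chance. A comparison that ignores the starting score then mixes the drug effect with that accident, and its interval is wider than the collected data require. Protocol 9.1 gives effect estimation as the focus, and 9.5 says the estimates are for planning future studies, so precision is the main thing the trial delivers. If adjustment is not pre-specified, adopting it after an imbalance has been seen would be post hoc.

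**Working it through.** **1. The plan's own figure.** Protocol 9.5: "Assuming 50% of the 20 randomized efgartigimod participants are CRESS responders", with a one-sided 95% Wilson lower bound of about 33%. With p = 0.5, n = 20, z = 1.645:

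(0.5 + z²/40 − z·√(0.25/20 + z²/1600)) / (1 + z²/20) = (0.5677 − 0.1960) / 1.1353 = 0.327. It reproduces.

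**2. Scale of the between-arm comparison.** Protocol 9.5: "Participants will be randomized in a 2:1 ratio (efgartigimod:placebo) to achieve approximately 15 randomized participants" in each IgG group, so about 20 versus 10. Using the protocol's CRESS rates (50% versus 24–32%) only to set the scale:

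- SE = √(0.5·0.5/20 + p(1−p)/10)
- p = 0.24 gives 17.5 points, 0.28 gives 18.1, 0.32 gives 18.5.

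**3. How far apart eligible participants can start (Table 5 weights, protocol 8.2.4).**

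- Cutaneous 1, biological 2: ESSDAI 3 + 2 = 5; clinESSDAI 3.
- Articular 2, cutaneous 2, glandular 2: ESSDAI 4 + 6 + 4 = 14; clinESSDAI 6 + 6 + 4 = 16.

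**4. Simple bound on the chance shift.** Divide participants into low and high starters, fraction f low, with a response gap g between them. The SD of the arm difference in f is √(f(1−f)(1/20 + 1/10)), and the 1-SD shift is g times that. For f = 0.5 the SD is √(0.25 × 0.15) = 0.194, so:

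- g = 30 points: shift 5.8
- g = 40 points: shift 7.7
- g = 50 points: shift 9.7

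**5. Continuous version.** The documents supply none of these inputs; all are assumed. Baseline ESSDAI = 5 + gamma, mean/SD pairs 8/3, 9/4, 10/4.5 and 11/5. Baseline-to-week-24 correlation r = 0.3 to 0.8. Mean change −3 or −4. No treatment effect. 20,000 simulated trials per case. Response probability given baseline b:

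Φ((4.5 − [mean + change + r(b − mean)]) / (SD·√(1 − r²)))

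The 1-SD shift is the SD over trials of the arm difference in mean response probability. The total SE is √(p(1−p) × 0.15), which is 16.6 to 19.4 points across cases.

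| r | 1-SD shift (points) | Share of variance |
|---|---|---|
| 0.3 | 3.1–4.5 | 0.03–0.05 |
| 0.5 | 4.8–7.3 | 0.08–0.15 |
| 0.7 | 6.8–10.3 | 0.17–0.30 |
| 0.8 | 8.0–12.0 | 0.23–0.41 |

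Example: mean 9, SD 4, r = 0.5, change −3. Response is 49% in the lower half of baseline and 24% in the upper half. Shift 5.9, total SE 18.6, share (5.9/18.6)² = 0.10.

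**6. Gain from adjustment.** Removing the imbalance share completely would divide the variance by 1/(1 − share), from 1/0.97 = 1.03 to 1/0.59 = 1.69. A fitted model must estimate its coefficients. Simulating the three-term Firth model at 20 versus 10, under similar but not identical assumptions, gave a variance ratio of about 1.05 to 1.55 and an average estimate within 1 point of the unadjusted one. In sample-size terms, 30 × 1.05 = 31.5 and 30 × 1.55 = 46.5 participants. An SE of 18 would become 18/√1.05 = 17.6 or 18/√1.55 = 14.5.

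**7. Overall CRESS.** The clinESSDAI item decides the result only when exactly two of the other four items respond. Under four assumed sets of independent item rates, that probability is 0.28 to 0.42. An item shift of 6 to 12 points therefore becomes 0.28 × 6 = 1.7 to 0.42 × 12 = 5.0 points. At an item shift of 3 it is about 1.

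**The case against.** **Between-arm analyses of the same scores already exist.** This is true of the continuous scores, where an MMRM of change uses more information than a cut at 5. Its model terms are not visible in the public text and are not counted as missing; nor is the hidden SAS code. The MMRM does not produce the below-5 comparison, however. If the ANCOVA sentence in protocol 9.3.3 was meant to reach responder endpoints, the readable SAP sections 14.2.1.1–14.2.1.2 do not carry it through.

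**The unadjusted comparison is valid.** This stands. Imbalance under randomisation is random, and its contribution is already inside the SE and the interval. A reader might infer that the placebo comparison is biased. The documents do not support that.

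**Most responder endpoints already use baseline.** This also stands. A reader might infer that the responder analyses as a whole ignore the starting score. In fact improvement of at least 3 points in ESSDAI or clinESSDAI, the ESSPRI response and most of STAR are changes from baseline, and the other four CRESS items refer to baseline values or baseline status. The point concerns two secondary endpoints and, diluted, one of five CRESS items.

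**The size rests on assumptions.** It does. At r = 0.3 the shift is only 3 to 4.5 points and the gain is slight.

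**This is a small proof-of-concept study with no formal hypothesis, and imbalance will be visible in the baseline table.** This lowers the priority. But seeing an imbalance does not correct for it, and extra Cochran-Mantel-Haenszel strata would be sparse at n = 30. That is why one small penalised model is suggested.

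**Conclusion.** The point holds for ESSDAI < 5 and clinESSDAI < 5. In the readable text their between-arm comparison uses screening IgG only, although the baseline value of the same score is available for everyone. The loss is one of precision and interpretability.

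Under the assumed correlations of 0.3 to 0.8, the 1-SD chance shift is about 3 to 12 percentage points against an SE of about 18, and adjustment cuts the variance by a factor of about 1.05 to 1.55. A reader might take some part of that range as a documented shift, or conclude that response is fixed mainly by the starting score. Neither follows, because the documents report no baseline distribution, no correlation and no response by baseline score.

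For overall CRESS the effect is small: about 2 to 5 points when the item shift is 6 to 12, and less below that. It does not call for a change to the primary analysis.

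**What to change.** In SAP 14.2.1.1 and 14.2.1.2, for ESSDAI < 5 and clinESSDAI < 5, pre-specify a supportive standardised risk difference (efgartigimod minus placebo, with 95% CI) and report it beside the planned IgG-stratified result. Obtain it from a Firth-penalised logistic model with arm, IgG stratum and the baseline value of the same score, and no other terms. Add one sentence to SAP 14.2.1.4 or 14.2.1.1 saying that the ANCOVA/MMRM provision covers the continuous scores and this model covers the two threshold endpoints.

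A version of the CRESS comparison adjusted for baseline clinESSDAI is optional and should be labelled supportive.

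Cost: SAP wording and a few table rows, with no new data. The downside is a model-based estimate from about 30 participants, which is why the model should stay at three terms and not replace the planned result.

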## 9.3.4. Exploratory Endpoint Analyses

Summary statistics will be provided for the continuous exploratory endpoints, with frequency tables generated for all categorical endpoints. Full details of the analyses will be included in the SAP.

### 9.3.5. Safety Analyses

Exposure to IMP will be summarized by treatment group, using the safety analysis set.

AEs will be classified using the latest version of the MedDRA classification system. Any AEs with missing severity or relationship to IMP will be classified as severe and treatment related, respectively.

Incidence and maximal severity of TEAEs, AESIs, and SAEs will be summarized descriptively. Multiple occurrences of a single PT in a participant will be counted only once at the maximum grade. Summaries by IMP relatedness will also be provided. Any AEs leading to death or IMP discontinuation will also be summarized.

Laboratory parameters, vital signs, and ECG data will also be analyzed descriptively.

Full details of the safety summaries will be provided in the appropriate SAP.

## 9.3.6. Other Analyses

Additional analyses of the week 16 efficacy results may be provided.

PK, PD, immunogenicity, and biomarker results will be analyzed descriptively.

Population PK/PD analysis may be performed based on the PK and PD data and reported separately.

# 9.4. Interim Analysis

An unblinded interim analysis may be conducted midcourse at the sponsor/designee's discretion. Results will be made available to senior sponsor/designee staff only while maintaining the blind for the sites and sponsor clinical team members.

# 9.5. Sample Size Determination

Participants will be randomized in a 2:1 ratio (efgartigimod:placebo) to achieve approximately 15 randomized participants with an IgG value at screening > 16.0 g/L and 15 participants without an IgG value at screening > 16.0 g/L.

Assuming 50% of the 20 randomized efgartigimod participants are CRESS responders, the 95% 1-sided confidence limit lower bound for the proportion of responders is approximately 33% (Wilson score interval). Placebo response rates ranging from 24% to 32% have been reported. Therefore the target sample size should provide sufficient precision of the efgartigimod treatment effect at week 24 for planning future studies.

# 10. SUPPORTING DOCUMENTATION AND OPERATIONAL CONSIDERATIONS

# 10.1. Appendix 1: Regulatory, Ethical, and Study Oversight Considerations

## 10.1.1. Regulatory and Ethical Considerations

This study will be conducted according to the protocol and the following:

- Consensus ethical principles derived from international guidelines including the Declaration of Helsinki and Council for International Organizations of Medical Sciences international ethical guidelines
- Applicable ICH GCP guidelines
- Applicable laws and regulations

The protocol, protocol amendments, ICF, IB, and other relevant documents (eg, advertisements) must be submitted to an IRB/IEC by the investigator and reviewed and approved by the IRB/IEC before the study is initiated.

Any amendments to the protocol will require IRB/IEC approval before implementing changes made to the study design, except for changes necessary to eliminate an immediate hazard to study participants.

Protocols and any substantial amendments to the protocol will require health authority approval before initiation except for changes necessary to eliminate an immediate hazard to study participants.

The investigator is responsible for providing the following:

- Providing written summaries of the status of the study to the IRB/IEC annually or more frequently according to the requirements, policies, and procedures established by the IRB/IEC
- Notifying the IRB/IEC of SAEs or other significant safety findings as required by IRB/IEC procedures
- Providing oversight of the conduct of the study at the site and adherence to requirements of 21 CFR, ICH guidelines, the IRB/IEC, European regulation 536/2014 for clinical studies, and all other applicable local regulations

## 10.1.2. Financial Disclosure

Investigators and subinvestigators will provide the sponsor with sufficient, accurate financial information as requested to allow the sponsor to submit a complete and accurate financial certification or disclosure statements to the appropriate regulatory authorities. Investigators are responsible for providing information on financial interests during the study and for 1 year after completion of the study.

The following information will be collected: any significant payments from the sponsor such as a grant to fund ongoing research, compensation in the form of equipment, retainer for ongoing

consultation or honoraria, proprietary interest in IMP, significant equity interest in the sponsor as defined in 21 CFR 54 2(b) (1998).

### 10.1.3. Informed Consent Process

The investigator or representative will explain the nature of the study, including risks and benefits to the potential participant, and answer all questions before the participant completes the informed consent process by signing the ICF.

Potential participants must be informed that their participation is voluntary. A statement of informed consent must be signed that meets the requirements of the IRB/IEC or study center, ICH guidelines, 21 CFR 50, local regulations, and, where applicable, privacy and data protection requirements.

The medical record must include a statement that written informed consent was obtained before the participant was enrolled in the study and the date the written consent was obtained. The authorized person obtaining the informed consent must also sign the ICF.

Participants must be reconsented to the most current version of the ICF(s) during their participation in the study if the changes to the ICF affect participant participation.

A copy of the ICF(s) must be provided to the participant (or their legally authorized representative).

Participants who are rescreened are required to sign a new ICF (Section 5.4).

## 10.1.4. Recruitment Strategy

Not applicable.

### 10.1.5. Data Protection

The sponsor will assign participants a unique identifier. Any participant records or datasets transferred to the sponsor will contain the identifier only; participant names or any information that would make the participant identifiable will not be transferred.

The participant must be informed that the sponsor, sponsor representatives, competent authorities, etc may review source data containing identifiers and will use their personal study-related data per local data protection law. The level of disclosure must also be explained to the participant who will be required to give consent for their data to be used as described in the ICF.

The contract between sponsor and study sites specifies responsibilities of the parties related to data protection, including handling of data security breaches and respective communication and cooperation of the parties.

Information technology systems used to collect, process, and store study-related data are secured by technical and organizational security measures designed to protect such data against accidental or unlawful loss, alteration, or unauthorized disclosure or access.

